4.8.6. Vital Signs

Vital signs include height (cm) (only at baseline), weight (kg), systolic blood pressure (mmHg), diastolic blood pressure (mmHg), heart rate (beats/min), pulse (beats/min), and temperature ($^{\circ}$ C) (only at baseline). They are assessed at Day 0, Week 6, Week 12, Week 24, and Week 52. Please see Appendix III for a description of parameter, unit and number of decimals to be displayed in summary tables.

Actual values and changes from baseline will be summarized at each visit, as done for laboratory data, for each vital sign parameter. Baseline is defined in section 4.2.12. Actual values of weight will also be summarised by category (<70 kg, \geq 70 kg) at each visit.

By-subject listings of vital signs measurements will be presented.

4.8.7. Electrocardiogram

Shifts from baseline to Week 52 or early termination visit and last available post-baseline value relative to the Overall interpretation categories Normal, Abnormal Non-Clinically Significant, and Abnormal Clinically Significant will be tabulated.

The number and percentages of subjects meeting the ICH E14 criteria [2] will also be described. All post-baseline QT, QTcB and QTcF interval values (including unscheduled) will be used.

Absolute QTc interval prolongation:

- QTc interval > 450
- QTc interval > 480
- QTc interval > 500

ECG data for each subject will be provided in data listings, including the finding description.

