2.5.4. Safety Endpoints

- Incidence of adverse events (AEs): by System Organ Class (SOC) and Preferred Term (PT) (Medical Dictionary for Regulatory Activities (MedDRA) coded term), by maximum severity, related to study drug, leading to study drug discontinuation, serious, leading to death, and adjudicated.
- Incidence of AEs of clinical interest: HF hospitalisation and CV death.
- Incidence of Special Situation Events.
- Incidence of event adjudication (Hospitalisation, Urgent HF visit and Deaths).
- Incidence of related AEs of special interest: Hypersensitivity reactions, Hypophosphatemia, Injection/infusion site reactions and Haemosiderosis.
- Clinical laboratory panels (absolute and change from baseline, incidence of laboratory abnormalities).
- Vital Signs (absolute and change from baseline).
- Electrocardiograms (incidence of electrocardiogram abnormalities, QTc measurement meeting ICH E14 criteria [2]).
- Prior, concomitant and newly started medications.

Note: biomarkers exploratory analyses will not be part of the CSR of the main study. They will be described in a separate biomarker SAP.

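### QTc is summarised only as post-baseline counts above 450, 480 and 500; without the baseline ECG the table cannot separate prolongation already present from prolongation that developed on study

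*SAP*

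**What the plan says.** SAP 4.8.7 plans two kinds of ECG summary. The first is a shift from baseline of the investigator's overall reading (normal, abnormal not clinically significant, abnormal clinically significant), in Tables 14.4.5.1 and 14.4.5.2. The second concerns the QT interval: "The number and percentages of subjects meeting the ICH E14 criteria [2] will also be described". The criteria stand under "Absolute QTc interval prolongation" and run from "QTc interval > 450" through 480 to "QTc interval > 500". On the data to be used, the section says: "All post-baseline QT, QTcB and QTcF interval values (including unscheduled) will be used". It sets no condition on the baseline value and plans no mean, no change from baseline and no change category. The table list has a single QT table, 14.4.5.3. Individual ECG data go to listings.

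The baseline value is available. Protocol 9.2.3.7 requires a 12-lead ECG at baseline and Week 52, the schedule of events adds one at early termination, and SAP 4.2.12 defines baseline.

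Other numeric safety measures are treated differently. SAP 2.5.4, 4.8.5 and 4.8.6 give laboratory values and vital signs as actual values and change from baseline. SAP 4.8.5 also gives phosphorus a shift table by numeric category, from baseline to the lowest post-baseline value. For ECG, SAP 2.5.4 names "incidence of electrocardiogram abnormalities, QTc measurement meeting ICH E14 criteria" and no change from baseline.

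**The concern.** A subject with QTc 470 at baseline and 460 at Week 52 counts as above 450. So does a subject who went from 430 to 460. The planned table cannot tell them apart. None of the 26 exclusion criteria in Protocol 5.3 sets a QTc limit, so prolongation before dosing is not screened out.

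A reader of the study report would see a percentage above each threshold in each arm and could not say how much of it predates study drug. A real difference could look small because both arms carry the same background, or a high percentage could cause alarm although it was there at randomisation. The between-arm comparison is not biased by baseline prevalence in a randomised 1:1 trial. What is lost is information and interpretability.

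**Working it through.** The plan gives no QTc figure, so there is nothing to reproduce. The thresholds are taken to be in ms. Every QTc input below is an assumption. The calculations show direction and a range, not an estimate for this trial.

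**1. Effect on the ratio.** Let b be the share above a threshold at baseline, s the share of those still above it later (the same in both arms), and let new crossing among the rest be 5% on placebo and 10% on FCM, a true ratio of 2.0. The planned proportions are b·s + (1−b)·0.05 and b·s + (1−b)·0.10. With b = 0.30 and s = 0.80:

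- placebo: 0.24 + 0.035 = 0.275
- FCM: 0.24 + 0.070 = 0.310
- ratio: 0.310/0.275 = 1.13

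For b = 10%, 20%, 30% and 50% the ratio is 1.36, 1.20, 1.13 and 1.06. With s = 100%, it falls from 1.31 at b = 10% to 1.05 at b = 50%.

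**2. Information under a mean shift.** Take baseline and Week 52 QTc as bivariate normal with common mean and SD and correlation ρ, a 7 ms shift on FCM, and n = 450 per arm with an ECG (assumed, out of 550 randomised).

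- Planned count: p0 = P(QTc > 450) on placebo and p1 the same after the shift, p̄ = (p0+p1)/2. Power = Φ{[(p1−p0) − 1.96·√(2p̄(1−p̄)/n)] / √[(p0(1−p0)+p1(1−p1))/n]}.
- Newly above: the same formula among the n(1−b) subjects per arm at or below 450 at baseline, using their conditional probabilities of crossing.
- Baseline-adjusted mean: SE = SD·√(2(1−ρ²)/n), power = Φ(7/SE − 1.96).

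Worked case, mean 440, SD 35, ρ = 0.60:

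- Planned count: p0 = 0.388, p1 = 0.466, ratio 1.20, power 66%.
- Newly above: 0.231 and 0.306 among those at risk, ratio about 1.33, power 51%.
- Baseline-adjusted: SE = 35·√(2·0.64/450) = 1.87 ms, 7/1.87 − 1.96 = 1.79, power 96%.

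| Mean, SD, ρ | Above 450 at baseline | Placebo subjects above 450 later who were already above | Planned count: ratio, power | Newly above only: ratio, power | Baseline-adjusted mean: power |
|---|---|---|---|---|---|
| 430, 30, 0.60 | 25% | 54% | 1.32, 75% | 1.46, 65% | 99% |
| 440, 35, 0.60 | 39% | 64% | 1.20, 66% | 1.33, 51% | 96% |
| 440, 35, 0.75 | 39% | 72% | 1.20, 66% | 1.42, 57% | 99% |
| 450, 40, 0.60 | 50% | 70% | 1.14, 55% | 1.25, 38% | 91% |

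The planned ratio lies nearer 1 than the newly-above ratio in every row. Yet the newly-above count has less power in every row, and also at 480 and 500, because a mean shift acts on already-prolonged subjects too and leaving them out discards data. Step 1 ranks the two counts the other way (with 550 per arm and s = 80%: 56%, 36%, 25% and 13% planned against 85%, 81%, 75% and 61% newly above), but only because it assumes no drug effect in subjects prolonged at baseline. So the ranking of the two counts depends on the model. The gain in the last column comes from using the numeric value together with baseline.

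**The case against.** Four points on the other side carry weight.

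- **The analysis is descriptive.** Protocol 12.8 presents safety data descriptively and does not list ECG among its safety outcomes. No QTc test is planned. This stands: the power figures measure lost information, not the failure of a planned test.
- **Timing.** The scheduled post-baseline ECG is at Week 52 or early termination, and the last possible scheduled dose is at Week 24, so a Week 52 ECG comes 28 weeks later. Protocol 1.2 gives a terminal half-life of about 16 hours, and the common adverse reactions it lists include no QT effect. This stands too. No rearrangement of these data can show a short-lived effect after dosing, and nothing in the documents points to a 7 ms effect at Week 52.
- **Baseline is used elsewhere.** The overall reading is shown as a shift, and Protocol 9.2.3.7 has clinically relevant new or worsened ECG findings reported as adverse events, which reach the treatment-emergent tables under SAP 4.8.2. This stands in part. Both routes rest on the investigator's judgement, and the overall reading can move for reasons other than QTc.
- **Magnitude.** Mean, SD, correlation and numbers with an ECG are all assumed. This stands; the size is unknown.

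Two stronger readings are tempting. A reader might infer that the SAP presents prevalence as incidence. The text does not support that: in SAP 2.5.4 the word stands before ECG abnormalities, and SAP 4.8.7 calls the QTc criteria absolute and counts subjects who meet them, without calling them new. A reader might also infer that counting only newly prolonged subjects would restore sensitivity. Under a mean shift it does the opposite.

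**Conclusion.** The point holds as a low-cost improvement to a descriptive safety table. Numeric QTc is the exception among the SAP's safety measures: a baseline value is collected and then left out of the summary, with no reason given. The resulting table cannot separate earlier from new prolongation, and in both illustrations its ratio lies nearer 1 than the ratio among subjects not prolonged at baseline.

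That direction rests on some subjects being above a threshold at baseline and on the relative effect being smaller among them than among the rest, as it is in both models. The size cannot be given from the documents. Nothing here shows that a QTc effect exists or would be missed, and no efficacy conclusion is touched.

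**What to change.** In SAP 4.8.7 and Table 14.4.5.3, for QTcB and QTcF separately:

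- Keep the planned counts and percentages above 450, 480 and 500, and state the unit.
- Lay them out by arm as a shift from baseline category (≤450, >450 to 480, >480 to 500, >500, missing) to the highest post-baseline category. New crossings can then be read off without replacing the absolute counts.
- Add actual value and change from baseline by arm at Week 52 or early termination and at the last post-baseline value, with a baseline-adjusted mean difference and 95% CI, labelled descriptive.
- Give the number of subjects with both a baseline and a post-baseline value. Deaths, and Week 52 visits held remotely as the COVID-19 note allows, can leave no ECG.
- Add a footnote that, apart from unscheduled recordings, the post-baseline ECG comes at Week 52 or early termination, so the table does not address short-lived effects after dosing.

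The cost is a few lines of SAP text and one extended table from data already collected. No visit, procedure or threshold changes. The phosphorus shift table in SAP 4.8.5 is a ready model for the layout.

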4.8.8. Concomitant Medications

For analysis, concomitant medications are defined as any medications other than IMP, which are taken any time on or after the date of the first IMP dose. Medications with a start or stop date on or after the first IMP dosing date will be considered concomitant medications. All medications categorised as ongoing at baseline will be considered concomitant medications. Newly started medications are defined as any medications other than IMP, which have an onset on or after the first IMP dose.

Prior medications are defined any medications which are taken any time prior to the first IMP dose (onset before first IMP dose).

Incomplete medication-related dates will be imputed temporarily in the following way in order to assign the medication to the appropriate categories

Medication start date:

- If the start date and end date of medication are missing completely then the medication start date will be imputed as the study drug start date.
- If the start date of a medication is missing completely, or is partially missing and the month and year or the year are equal to those of the first study drug start date and the medication end date is after or equal to the first study drug start date, then the medication start date will be imputed as the first study drug start date.
- If the medication end date is before the first study drug start date, the medication start date will be imputed as the medication end date if month and/or year is the same.
- Otherwise the month and/or day will be replaced by January and/or 1.

Medication end date:

- Incomplete end dates will be imputed as the last day of the month (if only the day is missing) or last day of the last month of the year (if day and month are missing) or the date of death, whichever is earlier.
- In all other cases the incomplete stop date will not be imputed and the stop date will be assumed to be missing.

All medications will be categorized according to a standard dictionary (World Health Organization [WHO] Drug Classification). Counts and percentages of subjects using each medication will be computed and summarized by treatment group, by Anatomical Therapeutic Chemical (ATC) level 2 and level 4 codes and Preferred Name; separate summaries will be prepared for prior, concomitant, and newly started medications. A subject will be counted only once per drug category even if more than one medication is used or the medication is reported more than once.

In addition, a table will be created containing a number of subjects with at least one medication in following categories: ACE inhibitors, Angiotensin II receptor blockers (ARB), Sacubitril-Valsartan (ARNI), Aldosterone Antagonists, Beta-blocking agents, Digitalis glycosides, Loop diuretics, Thiazide and thiazide-like diuretics, Ivabradine, Statin, Acetylsalicylic acid, Other antiplatelet drugs, Vitamin K antagonists, Direct thrombin inhibitors, Direct factor Xa inhibitors. Medications included in each category are listed in Appendix IV. The categories are defined by ATC levels 3, 4 and 5, as ATC level 5 is not available for this study, Sponsor's representative will review all medications and categories defined by ATC level 5 will be based on this review. This summary will be done for prior and concomitant medications.

The use of prior, concomitant, and newly started medications will be included in a by-subject data listing. The listing will identify which medications are prior and which are concomitant.

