9.2.3.8 Documentation of Concomitant Treatments

All medications and treatments prescribed at the moment of informed consent must be documented on the appropriate eCRF pages. In addition, treatments prescribed up to at least 3 months prior to obtaining the informed consent must be documented on the appropriate eCRF pages, irrespective if the treatment is still ongoing at the time of screening. This includes the recording in the eCRF of all medications/treatments prescribed for the AHF episode.

All changes to or addition of concomitant treatments as of informed consent must be recorded (including changes in dose, change in formulation, starting or stopping medications) in the eCRF. If the indication for changing a subject's concomitant treatment constitutes a new medical condition or a worsening of an existing clinical condition which is considered by the Investigator as being clinically relevant, the indication must be documented as an AE (see Section 10).

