- Subjects with triple therapy (defined as ACE or ARB or ARNI (any of these groups) and beta blockers and Aldosterone Antagonists) versus subject without the triple therapy

See section 4.8.8 and Appendix IV for definition of the medication of special interest categories. Medications will be considered for these subgroups if they were taken by the subject at the time of randomisation. Analyses for these six subgroups will not be part of the main set of outputs.

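### A background drug ongoing at baseline with no recorded start date is tabulated as newly started and dropped from prior medication

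*SAP*

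**What the plan says.** SAP 4.8.8 defines three overlapping categories. A medication is concomitant if it starts or stops on or after the first dose, or is categorised as ongoing at baseline. It is prior if taken before the first dose, with a bracketed condition that onset precedes that dose. The third category reads: "Newly started medications are defined as any medications other than IMP, which have an onset on or after the first IMP dose".

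The section then gives four start-date rules whose stated purpose is to assign medications to these categories:

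- First rule: where "the start date and end date of medication are missing completely then the medication start date will be imputed as the study drug start date".
- Second rule: for a start date that is wholly missing, or partial and matching the first-dose month and year or year, where "the medication end date is after or equal to the first study drug start date, then the medication start date will be imputed as the" date of first dose.
- Third rule: "If the medication end date is before the first study drug start date, the medication start date will be imputed as the medication end date", subject to a matching month or year.
- Fourth rule: in all other cases a missing month becomes January and a missing day becomes 1.

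SAP 2.5.4 lists "Prior, concomitant and newly started medications" among the safety endpoints. The SAP output list has prior tables by ATC code and by medication of special interest (14.1.9.1.x), and newly started tables by ATC code and preferred name (14.1.9.3.x).

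**The concern.** The first two rules place an unknown start exactly on the first-dose date. That date satisfies the newly started definition and fails the onset condition for prior. For a drug the subject was already taking, both results are wrong, and the section itself holds the information that shows it: the ongoing-at-baseline status.

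Records of this kind can be expected. Under Protocol 9.2.3.8, "treatments prescribed up to at least 3 months prior to obtaining the informed consent must be documented", and SAP 2.1 says that established heart failure therapy continues in all subjects. Long-term drugs are the ones whose start is most likely to be unknown.

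Two descriptions of the trial are at stake. The prior tables, including the table of heart failure drug classes, show what therapy subjects were on before dosing. The newly started tables show what was added afterwards, and Protocol 7.7.1 aims to keep the heart failure regimen as stable as the clinical picture allows. The first would be understated and the second overstated.

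**Working it through.** The plan gives no figure to reproduce. The check applies the four rules and the three definitions literally to test records. The first-dose date of 15 Nov 2018 is an assumption for illustration, and the pattern does not depend on it.

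| Record | Start recorded | End recorded | Rule | Start used | Prior | Newly started | Concomitant |
|---|---|---|---|---|---|---|---|
| 1 | none | none, ongoing at baseline | first | 15 Nov 2018 | no | yes | yes |
| 2 | none | 1 Jun 2019 | second | 15 Nov 2018 | no | yes | yes |
| 3 | none | 1 Nov 2018 | third | 1 Nov 2018 | yes | no | no |
| 4 | 2015 only | none, ongoing | fourth | 1 Jan 2015 | yes | no | yes |
| 5 | 2018 only | none, ongoing | fourth | 1 Jan 2018 | yes | no | yes |
| 6 | 2018 only | 1 Jun 2019 | second | 15 Nov 2018 | no | yes | yes |
| 7 | Nov 2018 | 1 Jun 2019 | second | 15 Nov 2018 | no | yes | yes |
| 8 | 4 Mar 2010 | none, ongoing | none needed | 4 Mar 2010 | yes | no | yes |

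**Records 1 and 2** are the fault. If the drug was ongoing at baseline, it was in use before dosing, yet it is sorted as newly started and not prior. SAP 4.2.12 does not rescue it. There, an assessment on the first study day with a missing time counts as pre-dose, but medications are expressly excepted and counted as concomitant.

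**Records 3, 4 and 8** are sorted correctly. For record 3 the third rule's month-or-year condition cannot be tested on a wholly missing start, but a drug that ended before first dose must also have begun before it.

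**Records 5 and 6** differ only in the end date. With none, the start becomes 1 January and the drug is prior. With a stop after first dose, the start becomes the first-dose date and the drug is newly started. A later stop date thus decides whether the drug counts as baseline therapy. The adverse-event rule in SAP 4.8.2 avoids this, because its end-date condition also covers a missing end date.

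**Scale.** Subjects count once per drug category. Where every record a subject has in a category is of type 1 or 2, the prior count falls by one. The newly started count rises by one, unless the subject also has a genuine new start in that category. With the planned 550 subjects per arm, one percentage point is 0.01 × 550 = 5.5 subjects. The documents do not say how many records lack a start date, so no percentage can be put on the error.

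**The case against.** **First-dose imputation is a common cautious convention, and the adverse-event rule does the same.** True, but the caution is there to avoid missing a concomitant drug. The ongoing-at-baseline status already secures that, so for these records the imputation only damages the other two categories.

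**The SAP never says that ongoing means a missing end date.** If it does not, the first rule may not reach record 1. The fourth rule cannot supply a missing year either, so the plan would have a gap instead of a wrong answer. This stands as an ambiguity for record 1. It does not touch record 2, where the end date is present and the second rule plainly applies.

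**Prior is defined first by being taken before the dose, which an ongoing drug satisfies.** The bracketed onset condition in the same sentence points the other way, and the imputed date is what gets tested against it. Even on the kinder reading, the drug would still be listed as newly started.

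**Few records may be affected.** Protocol 15.2.1 sends incomplete eCRF entries to query, 15.2.2 requires medication dates in source, and another dated record in the same class can keep a subject in the prior count. All of this stands. It limits how often the error occurs, not whether the rule is wrong when it applies.

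**Same-year partial dates prove nothing about long-standing drugs.** Agreed. A start recorded only as 2018 could fall on either side of the dose. Records 5 and 6 show inconsistent handling, not a demonstrably wrong category.

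**Conclusion.** The concern holds for one kind of record: a drug in use at baseline whose start date is wholly missing and whose end date is missing or on or after first dose. Such a drug is wrongly counted as newly started and wrongly left out of prior. The inconsistency for same-year partial dates is a second, lesser fault in the same rules. The conclusion rests on a literal reading of 4.8.8 and, for records without an end date, on ongoing being stored as a missing end date. The size is unknown.

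The consequence is limited to the descriptive prior tables, including the prior heart failure drug-class table, and the newly started tables. Affected drugs still appear correctly in the concomitant tables, and the efficacy analyses are not affected.

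A reader might infer three stronger things that the documents do not support:

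- That any incomplete start date causes the error. A known earlier start year is enough to keep the drug in prior.
- That a between-arm comparison of new starts would be distorted. SAP 4.8.8 plans only counts and percentages by group, with no test or ratio, and the drug-class table has no newly started version.
- That the exploratory treatment subgroups lose users. SAP 4.2.6 says: "Medications will be considered for these subgroups if they were taken by the subject at the time of randomisation". It does not say that imputed dates decide this, and 4.8.8 describes the imputation as temporary and for assigning categories.

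**What to change.** In SAP 4.8.8, ahead of the date rules, state that any medication categorised as ongoing at baseline is prior and concomitant and never newly started, whatever part of its start date is missing. Apply the first-dose imputation only to records without that status. For same-year partial start dates, use one rule whether the end date is present or missing.

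With this change, records 1 and 2 become prior and concomitant when they carry the ongoing-at-baseline status. Records 5 and 6 no longer differ because of the end date. The correctly sorted records stay as they are.

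The cost is a few sentences in the SAP and a few lines of derivation code. No new data should be needed, since the change uses only the status that 4.8.8 already names. It should be confirmed that the status is held in the database for every medication record.
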